## **18. QUALITY ASSURANCE**

The Research and Development (R&D) Quality Assurance Department of Chiesi may perform an audit at any time according to the Sponsor's Standard Operating Procedures, in order to verify whether the study is being conducted in agreement with GCP and the protocol.

## **19. INSURANCE AND INDEMNITY**

Chiesi holds and will maintain an adequate insurance policy covering damages arising out of Chiesi's sponsored clinical research studies.

Chiesi will indemnify the Investigator and hold him/her harmless for claims or damages arising out of the investigation, in excess of those covered by his/her own professional liability insurance, providing that the medication was administered under his/her or deputy's supervision and in strict accordance with accepted medical practice and with the study protocol.

The Investigator must notify Chiesi immediately upon notice of any claims or lawsuits.

## **20. CONFIDENTIALITY**

All study documents will be provided by the Sponsor in confidence to the Investigator and his/her appointed staff. None of this material may be disclosed to any party not directly involved in the study without written permission from Chiesi.

The Investigator must assure that the subject's anonymity will be maintained. The Investigator will keep a separate list with at least the initials, the subject's study numbers, names, and (optionally) his/her address and telephone number. The Investigator will maintain this for the longest period of time allowed by his/her own institution and, in any case, until further communication from Chiesi.

|  |                      |
|--|----------------------|
| Clinical Study Code No.: CLI-05993AB6-07 | Version No.: 2.0     |
| EUDRACT No.: 2022-000536-36              | Date: 30 August 2022 |

## **21. PREMATURE TERMINATION OF THE STUDY**

Both the Sponsor and the Investigator reserve the right to terminate the study at any time. Should this be necessary, the procedures for an early termination or temporary halt will be arranged after consultation by all involved parties.

The Sponsor should submit a written notification to the Regulatory Authority concerned and EC providing the justification of premature ending or of the temporary halt.

## **22. CLINICAL STUDY REPORT**

The Clinical Study Report, including the statistical and clinical evaluations, shall be prepared and sent to the Investigator for agreement and signature.

At the end of the trial, a summary of the CSR will be provided to all the ECs, to the UK Competent Authority and to the Investigators.

## **23. RECORD RETENTION**

After completion of the study, all documents and data relating to the study will be kept in an orderly manner by the Investigator in a secure study file.

Regulations require that essential documents must be retained for at least two years after the final marketing approval in an ICH region or until two years have elapsed since the formal interruption of the clinical development of the product under study.

It is the responsibility of the Sponsor to inform the Investigator of when these documents can be destroyed. The Investigator must contact Chiesi before destroying any trial-related documentation. In addition, all subjects' medical records and other source documentation will be kept for the maximum time permitted by the institution.

## **24. PUBLICATION OF RESULTS**

Chiesi is entitled to publish and/or present any results of this study at scientific meetings, and to submit the clinical trial data to national and international Regulatory Authorities and, if they fall under the Chiesi commitments on Clinical Trial Transparency, to make them available on [www.chiesi.com](http://www.chiesi.com) website.

Chiesi furthermore reserves the right to use such data for industrial purposes.

In the absence of a Study Steering Committee, Investigators will inform Chiesi before using the results of the study for publication or presentation and agree to provide the Sponsor with a copy of the proposed presentation. Data from individual study sites must not be published separately.

Negative, as well as positive results should be published or otherwise made publicly available according to the relevant regulatory requirements.

### Recommendations related to contraception and pregnancy testing in clinical trials

#### **Definition of women of childbearing potential, postmenopausal state and of fertile men**

For the purpose of this document, a woman is considered of childbearing potential (WOCBP), i.e. fertile, following menarche and until becoming postmenopausal unless permanently sterile. Permanent sterilisation methods include hysterectomy, bilateral salpingectomy and bilateral oophorectomy.

A postmenopausal state is defined as no menses for 12 months without an alternative medical cause. A high follicle-stimulating hormone (FSH) level in the postmenopausal range may be used to confirm a postmenopausal state in women not using hormonal contraception or hormonal replacement therapy. However, in the absence of 12 months of amenorrhea, a single FSH measurement is insufficient.

For the purpose of this document, a man is considered fertile after puberty unless permanently sterile by bilateral orchidectomy.

#### **Birth control methods, which may be considered as highly effective**

For the purpose of this guidance, methods that can achieve a failure rate of less than 1% per year when used consistently and correctly are considered as highly effective birth control methods. Such methods include:

- Combined (oestrogen and progestogen containing) hormonal contraception associated with inhibition of ovulation:
  - Oral;
  - Intravaginal;
  - Transdermal;
- Progestogen-only hormonal contraception associated with inhibition of ovulation:
  - Oral;
  - Injectable;
  - Implantable ;
- Intrauterine device (IUD) ;
- Intrauterine hormone-releasing system (IUS) ;
- Bilateral tubal occlusion ;
- Vasectomised partner ;
- Sexual abstinence .

 Vasectomised partner is a highly effective birth control method provided that partner is the sole sexual partner of the WOCBP trial participant and that the vasectomised partner has received medical assessment of the surgical success.

 Sexual abstinence is considered a highly effective method only if defined as refraining from heterosexual intercourse during the entire period of risk associated with the study treatments. The reliability of sexual abstinence needs to be evaluated in relation to the duration of the clinical trial and the preferred and usual lifestyle of the subject.

 Methods with lower user dependency.

*Reference: Recommendations related to contraception and pregnancy testing in clinical trials (Clinical Trial Facilitation Group. Final version 1.1 dd. 21/09/2020).*

Version or ID	Date (ddMMMyyyy)	Impact of the changes on the statistical analysis
Final 1.0	06APR2022	NAP
Final 2.0	30AUG2022	NAP

Protocol amendments:		
Version or ID	Date (ddMMMyyyy)	Impact of the amendment on the statistical analysis
NAP		

This statistical analysis plan (SAP) only considers the last version of the protocol, and of the protocol amendments, as listed above.

	Statistical Analysis Plan	
CLI-05993AB6-07		Final 1.0 of 22DEC2022

LIST OF ABBREVIATIONS

ACQ-5	Asthma Control Questionnaire [©]
ADaM	analysis data model
ADR	adverse drug reaction
AE	adverse event
ANCOVA	analysis of covariance
ATC	anatomical therapeutic chemical
AUC	area under the curve
AUC _{0-xh}	area under the curve, from 0 to x hours post-dose
BMI	body mass index
CI	confidence interval
COVID-19	coronavirus disease 2019
CPU	clinical pharmacology unit
CRF	case report form
DBP	diastolic blood pressure
DRM	data review meeting
DRR	data review report
DY	relative day
ECG	electrocardiogram
eCRF	electronic case report form
EMA	European Medicines Agency
ENR	enrolled set
FEV ₁	forced expiratory volume in 1 second
FSH	follicle-stimulating hormone
FVC	forced vital capacity
HFA	hydrofluoroalkane
HR	heart rate
ICF	informed consent form
ICH	International Council for Harmonisation of Technical Requirements for Pharmaceuticals for Human Use
KFR	key first results
MedDRA	Medical Dictionary for Regulatory Activities
NAP	not applicable
PEF	peak expiratory flow

	Statistical Analysis Plan	
CLI-05993AB6-07		Final 1.0 of 22DEC2022

pMDI	pressurised metered dose inhaler
PP	per protocol
QTc	corrected QT interval
QTcF	Fridericia's corrected QT interval
RND	randomised set
SAF	safety set
SAP	statistical analysis plan
SBP	systolic blood pressure
SD	standard deviation
SDTM	study data tabulation model
SE	standard error
█ CR	█ Clinical Research
SOP	standard operating procedure
STAT	Statistics
TEAE	treatment-emergent adverse event
TLF	tables, listings and figures
VS	vital signs
WHO	World Health Organisation
WHODrug	WHO drug dictionary
WI	work instruction

	Statistical Analysis Plan	
CLI-05993AB6-07		Final 1.0 of 22DEC2022

DEFINITION OF TERMS

bias	The systematic tendency of any factors associated with the design, conduct, analysis and evaluation of the results of a clinical trial to make the estimate of a treatment effect deviate from its true value. Bias introduced through deviations in conduct is referred to as 'operational' bias. The other sources of bias listed above are referred to as 'statistical'.
case report form (CRF)	A printed, optical, or electronic document designed to record protocol required information to be reported to the sponsor for each trial subject.
display	Analysis table, listing or figure
phase	Interval of time in the planned conduct of a study associated with a specific purpose: for example, screening, treatment, follow-up.
significant digit	All digits of a number used to express it to the required degree of accuracy, starting from the first non-zero digit.
standardised unit	unit populating --STRESU in the clinical database

Statistical Analysis Plan

CLI-05993AB6-07

Final 1.0 of 22DEC2022

1. INTRODUCTION

This SAP describes the final statistical analysis to be performed for the CLI-05993AB6-07 (BE-80-2100847) study.

This SAP covers the safety, [REDACTED], and general characteristics parts of the statistical analysis. It specifies the analysis displays to be presented and describes the methods and procedures in a more elaborated way than in the statistical methods section of the protocol.

The statistical analysis will process and present the results following the International Council for Harmonisation of Technical Requirements for Pharmaceuticals for Human Use (ICH) standards, in particular the ICH-E3, ICH-E6(R2), and ICH-E9 guidelines.

1.1 STUDY OBJECTIVES

According to the protocol, the primary objective of this study is:

- To compare the potential for bronchoconstriction [REDACTED] of the HFA-152a propellant versus [REDACTED] the HFA-134a propellant when administered alone (not in combination with other active compounds).

According to the protocol, the secondary objective of this study is:

[figure not shown]
- To evaluate the general safety and tolerability of the two different propellants.

1.2 STUDY DESIGN

This is a Phase IIa, multicentre, single-dose, randomised, double-blind, controlled, 2-way cross-over study to evaluate the potential for bronchoconstriction of the new HFA-152a propellant (single dose, [REDACTED]) versus the marketed HFA-134a propellant (single dose, [REDACTED]) in adult subjects with mild asthma.

A double-blind design was chosen for this study to minimise the risk of bias in the study outcomes.

The study design [1] is shown in the below figure:

HFA = Hydrofluoroalkane; pMDI = Pressurised metered dose inhaler.

[1] The study design proposed in the figure is just an example of one of the possible sequences.

[2] The pre-screening and screening visits can be combined in one visit if the study restrictions and wash-out requirements are respected at pre-screening.

[3] A follow-up visit can be performed, if deemed necessary by the Investigator.

The schedule of assessments is in appendix 9.2.

1.3 EXPECTED SAMPLE SIZE

The sample size has been calculated to verify equivalence between the test treatment (HFA-152a) and the reference treatment (HFA-134a) for the relative change from baseline in FEV₁ at the 15 min post-dose time point, with equivalence defined as a difference between the two treatments within the 10% (i.e. [-10%; +10%]).

A total of 20 evaluable subjects will ensure a 95% power to provide a 95% confidence interval (CI) of the mean difference of the relative change from baseline in FEV₁ at 15 min post-dose within the above-mentioned equivalence limits (i.e. [-10%; +10%]) assuming a within-subject standard deviation (SD) of 8%.

Estimating a non-evaluable rate of 16%, a total of 24 subjects will be randomised.

1.4 RANDOMISATION AND BLINDING

A balanced block randomisation list will be prepared using a computerised system. Each subject will be assigned to one of the two possible treatment sequences arranged in a 2x2 William design.

Each subject will be identified by a unique five-digit code assigned at screening.

At randomisation (TP1), each eligible subject will be assigned the lowest randomisation number available at the investigational centre according to a pre-established randomisation list.

1.5 INTERIM ANALYSIS

No interim analyses are foreseen.

	Statistical Analysis Plan	
CLI-05993AB6-07		Final 1.0 of 22DEC2022

1.6 SOFTWARE

SAS version 9.4 or later (SAS Institute Inc., Cary, NC, USA) will be used for programming.

1.7 VALIDATION MODEL

■ Statistics (STAT) standard operating procedures (SOPs) and work instructions (WIs) as effective at the time of the activity will be followed throughout the project, provided the applicable regulatory requirements are still met.

The analysis tables/figures/listings will be validated according to model B (review by an independent person; see SOP.STAT.020).

	Statistical Analysis Plan	
CLI-05993AB6-07		Final 1.0 of 22DEC2022

2. SAFETY ANALYSES

2.1 ADVERSE EVENTS

2.1.1 *Available data*

Adverse events (AEs) are coded into system organ classes and preferred terms using the medical dictionary for regulatory activities (MedDRA). For each AE, start and stop date(time)s are collected as well as severity, a seriousness flag, treatment-relationship, action taken towards the study drug and outcome.

2.1.2 *Derivation rules*

Pre-treatment AEs are defined as AEs starting between date of informed consent with 00:00 added as time part and the date(time) of first study drug administration – 1 minute, extremes included.

Treatment-emergent adverse events (TEAE) are defined as AEs starting on or after first administration of any study drug.

Adverse drug reactions (ADRs) are defined as TEAEs related to study drug or with missing relationship.

AEs of particular interest will be selected based on the following algorithms:

- Bronchospasm: to select preferred terms or lowest level terms including the word “bronchospasm”
- Cough: to select preferred terms or lowest level terms including the words “cough” or “coughing”
- Dysphonia: to select preferred terms including the word “dysphonia” (excluding lowest level terms containing the word “hoarseness”)
- Hoarseness: to select lowest level terms containing the word “hoarseness”

Based on their start date(time), AEs will be allocated to the phase and period during which they started. Phases and periods are defined in section 5.2.1. In case the AE start date(time) is incomplete or missing and the AE could consequently be allocated to more than one phase or period, a worst-case allocation will be done as detailed below:

- Treatment phase vs. non-treatment phase: AE will be allocated to the treatment phase.
- Multiple treatment periods: AE will be allocated to all treatment periods, except periods for which the available parts of the AE start or stop date(time) provides evidence the AE did not occur during that period.

A fatal AE is defined as an AE with outcome ‘fatal’.

An AE for which the study drug was discontinued is defined as an AE with action taken ‘drug permanently withdrawn’.

	Statistical Analysis Plan	
CLI-05993AB6-07		Final 1.0 of 22DEC2022

AE onset and duration will be calculated as follows:

- AE onset day (vs. first administration) =
 - AE start date < date of first administration: AE start date – date of first administration
 - AE start date \geq date of first administration: AE start date – date of first administration + 1 day
- AE onset day (vs. start of period) = AE start date – analysis period start date + 1 day
- AE duration (rounded as detailed in section 5.3.4) =
 - If start and stop date/time are available:
 - AE end date/time – AE start date/time + 1 minute
 - If only start and stop dates are available:
 - AE end date – AE start date + 1 day
 - date of last contact – AE start date + 1 day (when the AE start date is fully known but the AE is not resolved at the end of the study); in this case the duration will be presented as “>x days”.

2.1.3 Presentation of results

Tables will present TEAEs only. Pre-treatment AEs will only be listed.

An overview table will show the number and percentage of subjects with at least one event and the number of events by treatment and overall for the following:

- TEAEs
- Serious TEAEs
- Non-serious TEAEs
- ADRs
- Serious ADRs
- Severe TEAEs
- TEAEs leading to study drug discontinuation
- TEAEs leading to death
- TEAEs of particular interest

Separate summary tables by MedDRA system organ class and preferred term will show the number and percentage of subjects with at least one event and the number of events by treatment and overall for the aforementioned categories. Each AE record in the clinical database is considered as a distinct adverse event and is counted as such. Blank system organ classes and preferred terms, if any, will be shown as ‘Not Available’ in the tables and listings.

	Statistical Analysis Plan	
CLI-05993AB6-07		Final 1.0 of 22DEC2022

All AEs, including pre-treatment events and all coding information will be listed. COVID-19 related AEs will be flagged. Separate listings will be prepared for the categories presented in the summary tables.

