|  | 
be analysed using the same model used for the relative change from baseline in FEV1 at 15 min post-dose;
 

• The absolute changes from baseline in FEV1 at all post-dose timepoints (5 min, 15 min, 30 min, 1 h, 1 h 30 min and 3 h after T1) will be analysed using the same model used for the relative change from baseline in FEV1 at 15 min post-dose;

• The number and percentage of subjects with a relative change from baseline in FEV1 at each post-dose timepoint (5 min, 15 min, 30 min, 1 h, 1 h 30 min and 3 h after T1) and at any post-dose timepoint <-15% will be summarised for each treatment;

• The change from baseline in FEV1 AUC0-3h will be summarised using descriptive statistics;

• The relative and absolute changes from baseline in PEF at all post-dose timepoints (5 min, 15 min, 30 min, 1 h, 1 h 30 min and 3 h after T1) will be summarised for each treatment, using descriptive statistics;

• The number and percentage of subjects with use of rescue medication in the 3 h post-dose will be summarised for each treatment;

• The mean use (puffs) of rescue medication in the 3 h post-dose will be summarised for each treatment, using descriptive statistics.

 
Variables assessing the secondary objective of the study (general safety and tolerability of the two different propellants):
 

• The number of subjects who experienced at least one treatment-emergent adverse event (TEAE), adverse drug reaction (ADR), serious TEAE, serious ADR, TEAE leading to study discontinuation, and TEAE leading to death will be summarised for each treatment. Summaries will be presented overall (number and percentage of subjects having at least one event, total number of events) and by system organ class (SOC) and preferred term (PT) using the Medical Dictionary for Regulatory Activities (MedDRA). Specific summary tables will be provided for the AEs of particular interest.

 
All AEs will be listed.
 
Pre-treatment AEs will be listed only;
 

• The mean absolute values and mean changes from baseline in each 12-lead ECG parameter (HR, QRS, PR, and QTcF) will be summarised for each treatment, using descriptive statistics. For QTcF, the following categories will also be analysed for each study treatment, by means of descriptive statistics:

○ For male subjects: QTcF interval >450 ms, >480 ms and >500 ms;

○ For female subjects: QTcF interval >470 ms and >500 ms;

○ For both male and female subjects: Change from baseline >30 ms and >60 ms.

 
The analysis will be presented at each and any post-dose timepoint.
 
All data will be listed.
 |

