### **10.5 Action Taken with the Study Treatment Due to an Adverse Event**

- Dose not changed;
- Treatment permanently withdrawn;
- Unknown;
- Not applicable.

|  |                      |
|--|----------------------|
| Clinical Study Code No.: CLI-05993AB6-07 | Version No.: 2.0     |
| EUDRACT No.: 2022-000536-36              | Date: 30 August 2022 |

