- The mean use (puffs) of rescue medication in the 3 h post-dose will be summarised for each treatment, using descriptive statistics.

The safety variables assessing the **secondary objective** of the study (i.e. general safety and tolerability of the two different propellants) will be analysed as follow:

- **Adverse events and adverse events of particular interest:**

All AEs starting on or after the time of first study treatment intake will be classified as treatment-emergent adverse events (TEAE). Any AEs started after the informed consent signature and before the time of first study treatment intake will be classified as pre-treatment AEs.

The number of subjects who experienced at least one TEAE, ADR, serious TEAE, serious ADR, TEAE leading to study discontinuation, and TEAE leading to death will

|  |                      |
|--|----------------------|
| Clinical Study Code No.: CLI-05993AB6-07 | Version No.: 2.0     |
| EUDRACT No.: 2022-000536-36              | Date: 30 August 2022 |

be summarised for each treatment. Summaries will be presented overall (number and percentage of subjects having at least one event, total number of events) and by system organ class (SOC) and preferred term (PT) (number and percentage of subjects having at least one occurrence of that event) using the MedDRA. Specific summary tables will be provided for the AEs of particular interest (bronchospasm, cough, dysphonia, hoarseness).

All AEs will be listed.

Pre-treatment AEs will be listed only.

- **ECG**

For ECG parameters: HR, QRS, PR, and QTcF, mean absolute values and change from baseline will be summarised for each treatment using descriptive statistics. For QTcF, the following categories will also be analysed for each study treatment, by means of descriptive statistics:

- For male subjects: QTcF interval >450 ms, >480 ms and >500 ms;
- For female subjects: QTcF interval >470 ms and >500 ms;
- For both, male and female subjects: Change from baseline >30 ms and >60 ms.

The analysis will be presented at each post-dose timepoint and at any post-dose timepoint.

All data will be listed.

- **Vital signs**

Vital signs (SBP and DBP) mean absolute values at each pre-dose and post-dose timepoint and change from baseline will be summarised for each study treatment, by means of descriptive statistics.

All vital signs will be listed.

|              |
|--------------|
| • [REDACTED] |
| [REDACTED]   |
| • [REDACTED] |

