6. CHANGES TO THE PLANNED ANALYSIS

6.1 CHANGES NOT COVERED BY PROTOCOL AMENDMENTS BEFORE UNBLINDING

Not applicable

	Statistical Analysis Plan	
CLI-05993AB6-07		Final 1.0 of 22DEC2022

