14.3.1.8	TEAEs Leading to Study Drug Discontinuation by System Organ Class and Preferred Term (Safety Set) Tabulation of the number and percentage of subjects with TEAEs leading to study drug discontinuation by MedDRA system organ class and preferred term. The number of events will also be shown.	SAF	AET003
14.3.1.9	TEAEs Leading to Death by System Organ Class and Preferred Term (Safety Set) Tabulation of the number and percentage of subjects with TEAEs leading to death by MedDRA system organ class and preferred term. The number of events will also be shown.	SAF	AET003
14.3.1.10	TEAEs of Particular Interest (Safety Set) Tabulation of the number and percentage of subjects with TEAEs of particular interest (as defined in section 2.1.2) by MedDRA system organ class and preferred term. The number of events will also be shown.	SAF	AET003
VITAL SIGNS			
14.3.5.1	Vital Signs: Summary of Actual Values and Changes from Baseline (Safety Set) Descriptive statistics of vital signs actual values and changes from baseline per parameter and analysis time point. Table sorted by analysis time point. Each parameter will begin on a new page.	SAF	VST001
ECG			
14.3.6.1	Local 12-Lead ECG: Summary of Actual Values and Changes from Baseline (Safety Set) Descriptive statistics of continuous 12-lead ECG (HR, PR, QRS, QTcF) actual values and changes from baseline per analysis time point. Table sorted by analysis time point. Each parameter will begin on a new page.	SAF	EGT002
14.3.6.2	QTcF: Abnormalities (Safety Set) Tabulation of the abnormalities as defined in section 2.4.2 at baseline and each post-dose analysis time point and at the worst-case analysis time-point. Table sorted by analysis time point. Only baseline and post-dose analysis time points are shown.	SAF	EGT007
14.3.6.3	QTcF: Abnormal Changes from Baseline (Safety Set) Tabulation of the QTcF change abnormalities as defined in 2.4.2 at each post-dose analysis time point and at the worst-case analysis time point. Table sorted by analysis time point. Only post-dose analysis time points are shown.	SAF	EGT008

	Statistical Analysis Plan	
CLI-05993AB6-07		Final 1.0 of 22DEC2022

Number	Title	Analysis Set	TLFs Library Template Number
LUNG FUNCTION			
14.3.7.1.1	Lung Functions: Summary of Actual Values and Changes from Baseline (Safety Set) [KFR]	SAF	TPT001

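### The protocol promises a summary of adverse events leading to study discontinuation; the SAP tabulates only those leading to study drug discontinuation, and in this single-dose crossover the two need not coincide

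*SAP*

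**What the plan says.** Protocol section 12.3.6 lists what will be summarised for each treatment: "The number of subjects who experienced at least one TEAE, ADR, serious TEAE, serious ADR, TEAE leading to study discontinuation, and TEAE leading to death". The summaries are to be given overall and by system organ class and preferred term. The Protocol Outline repeats the commitment: "serious ADR, TEAE leading to study discontinuation, and TEAE leading to death will be summarised for each treatment".

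SAP section 2.1.3 gives the corresponding overview row as "TEAEs leading to study drug discontinuation". Section 8.1 carries the same category into Table 14.3.1.8, "TEAEs Leading to Study Drug Discontinuation by System Organ Class and Preferred Term (Safety Set", and Listing 16.2.7.8 follows it. The selection rule is in SAP section 2.1.2: "An AE for which the study drug was discontinued is defined as an AE with action taken", followed by the label 'drug permanently withdrawn'. No adverse event table in the SAP covers discontinuation of the study.

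SAP section 6.1, headed "CHANGES NOT COVERED BY PROTOCOL AMENDMENTS BEFORE UNBLINDING", contains only the entry 'Not applicable'.

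**The concern.** Stopping the drug and leaving the study are different events, recorded in different places. Protocol section 10.5 records what was done with the treatment because of the event. Protocol section 4.4 treats withdrawal as a separate decision and has its main reason entered on the Study Termination page.

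In a trial of daily dosing the two usually move together. Here each period is one administration, to be completed within 12 minutes. When an event starts after the last inhalation, that dose can no longer be changed. A site may then regard the action-taken question as not applicable and still withdraw the subject.

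At stake is a secondary safety output. Every outcome in this trial is a safety outcome, and tolerability is the secondary objective. The by-treatment summary of events that made subjects leave the study is one of the few adverse event outputs that the protocol names. As planned, that summary would not be produced, and the report would not say so.

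**Working it through.** The plan gives no figure to reproduce. The check is a comparison of definitions, followed by a size.

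**Inputs**
- Promised category: event leading to study discontinuation (Protocol Outline; Protocol 12.3.6).
- Planned category: event with action taken 'drug permanently withdrawn' (SAP 2.1.2, 2.1.3; Table 14.3.1.8).
- Action-taken options (Protocol 10.5): dose not changed; "Treatment permanently withdrawn"; unknown; not applicable. The section does not tell sites which to choose when a later period is cancelled.
- Other actions (Protocol 10.6): medication or procedure. Neither records study withdrawal, and nor do the adverse event fields listed in SAP 2.1.1.
- Study withdrawal and its reason: Study Termination page (Protocol 4.4).
- Time on study after the last dose: until the follow-up contact, 7 to 10 days after TP2.
- Randomised: 24. Evaluable target: 20 (Protocol 12.1).

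**Step 1. Apply both definitions to the cases that can arise**

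| Case | Action taken as coded | Protocol category | SAP category |
|---|---|---|---|
| A. Event after a completed TP1 dose; subject withdrawn before TP2 | permanently withdrawn | counted | counted |
| B. Same event and withdrawal | not applicable, or dose not changed | counted | not counted |
| C. Event after a completed TP2 dose; subject withdrawn before the follow-up contact | not applicable, or dose not changed (no dose remains) | counted | not counted |
| D. Intake stopped during dosing for severe cough (Protocol 6.2.3.1); subject remains in the study | permanently withdrawn | not counted | counted |

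A and B are the same clinical course and differ only in coding. D depends on the site's entry and on the subject remaining, because that section does not say that the subject leaves the study. Neither category contains the other, so the SAP's version is not a stricter or looser form of the protocol's.

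**Step 2. Find where a case B or C subject would still be visible**
- Tables 14.1.1.2 and 14.1.1.3: reason for discontinuation by sequence and by treatment.
- Listing 16.2.1.2: all discontinuations after randomisation, with the reason.
- Listing 16.2.1.3: the event itself, when it caused the discontinuation.
- Table 14.3.1.2: the event by class and term. Table 14.3.1.10 as well, if it is bronchospasm, cough, dysphonia or hoarseness. Neither depends on action taken.

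The subject is missing only from the drug-discontinuation row of Table 14.3.1.1, from Table 14.3.1.8, and from the matching Listing 16.2.7.8.

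**Step 3. Size**

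One missed subject as a share of those on the treatment = 1/n.
- n = 24: 1/24 = 0.0417, or 4.2%.
- n = 20: 1/20 = 0.050, or 5.0%.

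SAP 5.4.1 takes as denominator the subjects in the analysis set, phase and period, so n may be below 24 for a given treatment.

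**Step 4. Check how a new category would be allocated to treatment**

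SAP 2.1.2 allocates an adverse event to the period in which it starts. Under SAP 5.2.1, Period 1 runs until one minute before the second administration, or to last contact if there is none. Cases B and C therefore fall under the treatment just received. The choice of rule matters when an event starts after TP1, TP2 is given, and the subject is later withdrawn for that event. Allocation by last treatment received would then put the event under one propellant in Table 14.3.1.2 and under the other in the new table.

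**The case against.** The strongest answer is that the missed case depends on a coding choice that the documents do not settle. Study treatment is two administrations, supplied as one subject box holding two period boxes. If an event cancels TP2, part of the study treatment has been withdrawn, and permanent withdrawal is arguably the most natural of the four entries. The SAP rule then captures the subject. This stands in part: it makes case A at least as plausible as case B, and the eCRF completion instructions that would decide it are not in the documents. It does not dispose of case C, where no treatment remains. Nor does it explain why SAP 6.1 is silent.

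A second answer is that little is lost. Disposition by treatment, the listing that names the event and the general tables leave a reader able to reconstruct each withdrawal. In a trial of 24 subjects such withdrawals may be few, and a listing can convey almost as much as a table by class and term. This stands, and it limits the weight of the point.

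A reader might go further and infer that a withdrawal for bronchospasm on one propellant would vanish from the report, or be reported as 0%. The documents do not support that. The zero could appear in one overview row and one table, while the withdrawal, its treatment and its event would be shown elsewhere.

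**Conclusion.** The mismatch is certain on the text: a category promised in the protocol is replaced in the SAP by a different one, and the change is not declared. The consequence is conditional. It needs a subject withdrawn for an adverse event after a completed dose, with the action coded as something other than permanent withdrawal. If that happens, each such subject is understated by 1/24 = 4.2% (5.0% if 20 are exposed) in one row of Table 14.3.1.1 and in Table 14.3.1.8, and those outputs may disagree with the disposition tables. The 1/24 is the arithmetic of a single hypothetical subject, not a forecast. The primary FEV1 analysis is unaffected. This is a minor reporting gap, worth closing because doing so costs almost nothing.

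**What to change.** - In SAP 2.1.2, define a treatment-emergent event leading to study discontinuation from the Study Termination reason (adverse event) and the event linked to it. Listing 16.2.1.3 already needs that link, so no new data collection should be required. This assumes that the link is held in the database and not reconstructed by hand.
- Allocate it to treatment by the existing period-of-onset rule in SAP 2.1.2, so that it agrees with the other adverse event tables.
- Add the category to SAP 2.1.3 and Table 14.3.1.1, and show it by system organ class and preferred term alongside Table 14.3.1.8 or in its place, with a matching listing.
- Keep the action-taken category as an additional row if wanted, and declare it in SAP 6.1 as an addition to the protocol.
- Align the SAP's label 'drug permanently withdrawn' with the protocol option "Treatment permanently withdrawn", so that the selection does not depend on how the eCRF term was mapped.

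The cost is a few lines of SAP text, one derived flag, and one further table and listing built on an existing template. It should be done before the blind is broken.
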